5.6.2 Enrollment, Baseline, and/or Randomization

A. Enrollment Period

Baseline visit 1

- Fasting laboratory studies*
- Review and discussion of medication tapering if needed (by physician)
- Brief exam and standardized blood pressures
- Medical history, including evaluation of concomitant medications, adverse events for baseline
- **Laboratory Tests:** includes complete blood count, serum creatinine and blood urea nitrogen, glucose, ALT, urinalysis, total cholesterol, LDL and HDL cholesterol and triglycerides (fasting)
- **Baseline MRI** – (Radiology) Note: if patient has no WMH on baseline MRI, they will be excluded from further participation in the trial. No medication tapering will occur prior to the results of this study.

Baseline visit 2– this visit will be the first assessment following taper of prior antihypertensive therapy for those patients demonstrating WMH on the screening MRI.

- Medical history (intercurrent illnesses, medication history, adverse events)
- Standardized clinic BPs*

If patient is off antihypertensive agents at baseline or has been discontinued for 2 weeks with a mean clinic SBP \geq 150 mmHg, patient will proceed with various tests below. If SBP < 150 mmHg, patient will return in 1 week to re-evaluate clinic BPs.

- *Standardized clinic BP measurements will be taken using the validated Suntech Medical Instruments TM24/7 in the non-dominant arm, seated position in duplicate and 1 upon standing prior to dosing of morning BP medications.
- Ambulatory BP monitoring
- Home BP monitoring – self-monitoring with a portable digital device, obtaining BP readings twice-daily in duplicate (morning, evening) for seven days. Patients will receive training on proper use of the device and record readings on separate sheet. Blood pressure readings will be obtained in the seated position prior to any morning and/or evening antihypertensive medications.
- Mobility battery - Gait Speed, Stair ascent and descent, Supine-to-sit, Sit-to-stand, Functional reach, Stance time, Single leg stance
- Cognitive battery – HVLIT, Trail Making Test, Digit Span Test (Forward and Backward), Digit Span, Stroop Color and Word Test, Symbol Digit Substitution, Controlled Oral Word Association Test, California Computerized Assessment Package (Cal CAP), Geriatric Depression Scale.
- Incontinence questionnaires - UI 31Q, Urinary Incontinence Severity Index, Urogenital Distress Inventory (UDI), IIQ-7
- Mini-mental status exam

At this point, if all inclusion and exclusion criteria have been met, patient will be randomized to either A) Intensive ABP reduction group or B) Standard ABP reduction group. Treatment initiation will be as outlined in Section 5.1.

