4.2 Exclusion Criteria

All candidates meeting any of the following exclusion criteria at baseline will be excluded from study participation.

- 1) Uncontrolled diabetes mellitus (HBA1c >10%)
- 2) History of stroke, dementia or clinically impaired gait (Mini-mental status exam score (MMSE) <24, Short Physical Performance Battery for gait (SPPB) < 9,)
- 3) Body Mass Index > 45 kg/m² and/or arm circumference > 44 cm)
- 4) Poor kidney function (defined as estimated GFR <30 ml/minute)
- 5) Active liver disease or serum transaminases >3 times the upper limit of normal
- 6) Major cardiovascular event (e.g. myocardial infarction) or procedure (e.g. cardiac bypass surgery) in past 3 months; stroke with residual gait abnormality
- 7) Uncompensated congestive heart failure (NYHA class III or IV or documented ejection fraction <30%)
- 8) Chronic atrial fibrillation that disallows ambulatory BP monitoring to be successfully performed
- 9) Medical conditions that limit survival to < 3 years
- 10) Non-dermatologic cancer diagnosed within 2 years
- 11) Organ transplantation requiring anti-rejection drug therapy
- 12) Severe and unexplained weight loss (>15%) in past 6 months
- 13) Medical need to undergo recurrent phlebotomy or blood transfusions
- 14) Current participation in another investigational trial
- 15) Unable to obtain informed consent

- 16) Factors limiting adherence to the interventions
- 17) MRI contraindications (including MRI-incompatible implants, severe claustrophobia).
- 18) Known carotid or intracranial arterial occlusive disease.

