4.3 Study Enrollment Procedures at University of Connecticut Health Center

Study recruitment and enrollment. The study is a single-site randomized clinical trial that will be performed at the University of Connecticut Clinical Research Unit. Patients will be recruited from a variety of sources as described below. Three hundred patients will be enrolled into the trial in order to randomize 200 patients and complete 140 patients at 3 years of randomized treatment. Based on our prior experience in studying patients in this age group with hypertension and mild mobility issues, we project a 3-year attrition rate of approximately 30%. Recruitment will be carried out by several mechanisms, including: A) contacting former research participants from the Cardiology and Hypertension faculty practices, the Center on Aging, and Neurology who have agreed to be informed of future studies, B) publically posted advertisements in addition to advertisements on the internet, radio and newspapers, C) Recruitment presentations conducted at community health centers, faith-based organizations and senior centers in conjunction with BP community clinics.

Recruitment will be extended into the greater Hartford region to improve minority participation. Advertisements will state that we are seeking volunteers for a treatment study aimed at older patients with hypertension willing to join a study involving the evaluation and treatment of high blood pressure, mobility and cognitive function. The

ads will state that antihypertensive medication, clinical visits, brain imaging, and other testing will be provided at no cost.

Following voluntary assent, interested individuals will be screened by phone for inclusion/exclusion criteria. Those meeting initial screening criteria will be invited to a Consent/Evaluation Visit during which informed consent will be obtained, followed by a medical history, physical exam, and tests to determine eligibility. Those not meeting study criteria will be referred for medical care. Patients not able to read and understand the consent form will be excluded from the study.

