5.6.1 Screening Evaluation

Consenting Procedure

Consent authorization will not be obtained prior to preliminary screening through telephone calls initiated by potential subjects or for those interested in completing a brief screening questionnaire in person at community presentations. Those deemed eligible will sign a consent form at their first study visit.

Patients will be given time in the interview room privately to read the study consent form. After approximately 15-20 minutes, the study nurse or physician will review each section of the consent form together, taking time to answer any questions that arise. After any questions have been answered the study nurse or physician will move to the next section of the document and repeat the process. After the last section has been reviewed the patient will be asked to review the research project in his/her own words. If the subject provides an accurate summary s/he will be asked if s/he would like more time to consider their decision to participate and whether s/he would like to sign and date the consent form. If the summary is not accurate the coordinator will go over the relevant sections again. It is estimated that the informed consent discussion will take 30 to 45 minutes.

Signed consent forms will be stored securely in a locked file, separate from case report forms. Should significant findings arise that might affect a patient's willingness to continue to participate, the PI will submit a request for modification to the Informed Consent Form to the IRB and then, after obtaining approval, re-consent the subjects at the next regularly scheduled visit. If the updated consent form has not yet been approved by the IRB at the time of the visit a verbal explanation of the information will be provided to the patient and documentation of the explanation will be noted in the research record.

If the investigator or IRB determine that patients need to be contacted immediately depending on the nature of the information and the level of risk it

presents to subjects, the PI will communicate the information to the patients in the study as soon as possible and will document the contact with the patients.

Screening Procedures

- Study overview and consent
- Medical history
- Physical exam
- Standardized Clinic BPs
- ECG

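### The MMSE, an exclusion test, is itemised only after the antihypertensive taper, so a treated patient could lose therapy and then be excluded by a test that could have come first

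*Protocol*

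**What the plan says.** Protocol 4.2, criterion 2, sets these exclusion thresholds: "Mini-mental status exam score (MMSE) <24, Short Physical Performance Battery for gait (SPPB) < 9". Protocol 4.1, criterion D, admits patients taking up to two antihypertensives, or up to one if systolic BP is above 170 mmHg.

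Protocol 5.6.1 lists the screening procedures: overview and consent, history, physical exam, clinic BP and ECG. Protocol 5.6.2 lists for baseline visit 1 the laboratory tests, the discussion of tapering, a brief exam, history and the MRI. Neither list contains the MMSE. Under the MRI item the protocol adds: "No medication tapering will occur prior to the results of this study".

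Baseline visit 2 is introduced with the words "this visit will be the first assessment following taper of prior antihypertensive therapy for those patients demonstrating WMH on the screening MRI". Its tests go ahead if the patient is off drug at baseline or "has been discontinued for 2 weeks with a mean clinic SBP" of at least 150 mmHg. If the pressure is lower, the patient comes back a week later. The last item on the visit 2 list is "Mini-mental status exam". Next comes the final eligibility check: "At this point, if all inclusion and exclusion criteria have been met, patient will be randomized".

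The table in Protocol 5.5 allows 0 to 4 weeks for the washout. It has no MMSE row, and before randomisation it marks cognitive tests only under Baseline II.

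**The concern.** Some baseline measurements have to follow the taper. Untreated clinic systolic BP is itself an entry criterion, and baseline ambulatory BP is meant to be taken off drug. The MMSE is different. Its cut-off makes no reference to untreated pressure, and nothing in the documents says that it must be done off drug.

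The protocol already accepts the principle at stake: treatment is not withdrawn until the MRI shows that the patient has qualifying lesions. The same protection is not written for the MMSE. The people exposed are hypertensive, aged 75 or older, and selected for visible cerebrovascular disease on MRI. What is at stake is a small, avoidable safety exposure in patients who would gain nothing from the withdrawal. The validity of the trial is not at stake.

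**Working it through.** **Order of procedures.** This part needs no arithmetic.

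| Step | Where | MMSE named? | Patient on prior drugs? |
|---|---|---|---|
| Phone screen, Consent/Evaluation Visit | 4.3 | No (tests unnamed) | Yes |
| Screening list | 5.6.1 | No | Yes |
| Baseline visit 1, including MRI | 5.6.2 | No | Yes |
| Taper, conditional on MRI result | 5.6.2, 5.5 | Not a condition | Being withdrawn |
| Baseline visit 2 | 5.6.2 | Yes, last item | No, for 2 weeks or more |
| All criteria confirmed | 5.6.2 | Applied here at the latest | No |

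Read literally, a treated patient first meets the MMSE after at least 2 weeks off drug (5.6.2), with a washout of up to 4 weeks (5.5).

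**Size.** The plan gives no figure to reproduce. Two inputs are needed and neither is in the documents, so both are assumptions:

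- t = share of patients reaching visit 2 who were tapered: 25% to 75% (not 100%, because untreated patients are admitted).
- f = share of those at visit 2 who score below 24: 0.5% to 2%, taken as equal in treated and untreated patients.

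If the MMSE is the only remaining reason for failure, reaching 200 randomised takes 200/(1 − f) patients at visit 2. Of these, 200f/(1 − f) fail, and a share t of the failures had been tapered:

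withdrawn and then excluded = 200 × t × f/(1 − f)

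| f | t = 25% | t = 50% | t = 75% |
|---|---|---|---|
| 0.5% | 0.25 | 0.50 | 0.75 |
| 1% | 0.51 | 1.01 | 1.52 |
| 2% | 1.02 | 2.04 | 3.06 |

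In patient-weeks off therapy, at 2 to 4 weeks each:

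- lowest: 0.25 × 2 = 0.5
- middle: 1.01 × 2 = 2.0 to 1.01 × 4 = 4.0
- highest: 3.06 × 4 = 12.2

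The formula leaves out tapered patients who fail the BP criterion and would also have scored below 24. An early MMSE would spare them too.

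**Extra tests if the MMSE is moved earlier.** Randomised patients have the same single MMSE as now. Extra tests fall only on those never randomised: at most 300 − 200 = 100 (300 screened, Protocol 4) or 400 − 200 = 200 (400 screened, Précis). If the MMSE follows the MRI result, Protocol 4's expectation that two in three have lesions gives 300 × 2/3 = 200, which leaves almost no extra tests. That figure is approximate, since it allows for no later failures.

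**The case against.** The strongest reply is that the visit lists are plainly incomplete, so the absence of an early MMSE proves little. HbA1c above 10% is an exclusion, yet HbA1c is in neither laboratory list (5.6 and 5.6.2). The SPPB is an exclusion test that no visit names. The MRI is marked under Screen in the 5.5 table but is missing from the list in 5.6.1. Protocol 4.3 describes a phone screen and then a consent visit with "a medical history, physical exam, and tests to determine eligibility". During consent, "the patient will be asked to review the research project in his/her own words", which would catch some impaired patients. An MMSE next to the baseline cognitive battery also gives a current check just before randomisation.

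Much of this stands. A reader might infer that patients are in fact tapered before anyone tests their cognition. The documents do not support that, because the tests in 4.3 are unnamed and an earlier MMSE may be among them. What remains is that no text requires it, and the one placement that is written comes after the taper. A wish for a current score does not explain why the taper should start before any score is known.

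A reader might also infer that the SPPB comes too late and should be moved in the same way. That does not follow. Its timing is unspecified, and Protocol 5.6 cites it only to describe three stance postures. Requiring it early would have some later-randomised patients repeat gait tasks shortly before the baseline for gait velocity, the primary outcome (Protocol 8.2, Hypotheses and Statistical Analyses).

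**Conclusion.** The point holds as a gap in the written order. The only itemised MMSE follows the taper, and only the MRI result must precede it. A treated patient could therefore be off therapy for about 2 to 4 weeks and then be excluded on a test that could have been done first. That the MMSE does not need the untreated state is an inference from its cut-off; the protocol does not say so.

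The number affected cannot be derived from the documents. Under the assumed ranges it is about 0.3 to 3 patients, with a middle case of about 1 patient and 2 to 4 patient-weeks. The phone screen, the history and the dementia exclusion make a low figure likely.

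A reader might infer that ineligible patients could be randomised or that the comparison is biased. Neither is supported: all criteria must be met before randomisation, so bias and power are untouched. Nor is all withdrawal before final eligibility avoidable, since untreated systolic BP is a criterion. This is a cheap improvement to patient protection, not a flaw in the trial's inference.

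**What to change.** 1. List the MMSE at screening or baseline visit 1 (5.6.1 or 5.6.2) in place of its entry at visit 2.
2. Extend the taper sentence in 5.6.2 so that no medication is withdrawn until both the MRI and the MMSE results are known and qualifying.
3. Add an MMSE row to the table in 5.5.

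The outcome batteries stay at visit 2, and the handling of the SPPB is left as it is.

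The cost is a few lines of protocol text and a table edit. For the 200 randomised patients the test is moved, not added, and neither document gives the MMSE a role as an outcome. The extra burden is a short test in at most 100 to 200 patients who are never randomised, and in very few if it follows the MRI result. If staff already give the MMSE early, the change only records what they do. The SAP is dated September 2018, just before the planned database lock, so enrolment has presumably ended. The change then serves the plan as written and any protocol that reuses this screening sequence.

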5.6.3 Post-Randomization Follow-up Visits

Visit 1 (1 month post-randomization) – At visit 1, patients will be evaluated for their clinic BP responses to assigned therapies. Procedures previously defined above will be repeated at this visit:

- Medical history, concomitant medications, adverse events, medication compliance
- Standardized clinic BP measurements, body weight and height
- Antihypertensive medication titration as appropriate based on clinic systolic BP (goals are < 135 mmHg if assigned to the Intensive group and < 150 mmHg if assigned to the standard group)
- Dispense medications for next month

Visit 2 (2 months post-randomization) – Patients will return for evaluation of antihypertensive response to therapy according to randomized treatment group. Procedures previously defined above will be done at this visit:

- Medical history, concomitant medications, adverse events, medication compliance
- Standardized clinic BP measurements, body weight and height
- Antihypertensive medication titration or down-titration as appropriate (goals are < 135 mmHg if assigned to the Intensive group and < 150 mmHg if assigned to the standard group; if the standard BP group patient has a systolic BP < 135 mmHg, antihypertensive medications will be reduced by the study physician)
- Safety laboratory studies (potassium, creatinine, BUN) if clinically necessary
- Electrocardiogram if clinically necessary
- Dispense medications for next month

Visit 3 (3 months post-randomization) – Patients will return for evaluation of antihypertensive response to therapy according to randomized treatment group. Procedures previously defined above will be done at this visit:

- Medical history, concomitant medications, adverse events, medication compliance
- Standardized clinic BP measurements, body weight and height
- Antihypertensive medication titration or down-titration as appropriate (goals are < 135 mmHg if assigned to the Intensive group and < 150 mmHg if assigned to the standard group; if the standard BP group patient has a systolic BP < 135 mmHg, antihypertensive medications will be reduced by the study physician)
- Safety laboratory studies (potassium, creatinine, BUN) if clinically necessary
- Electrocardiogram if clinically necessary
- Ambulatory blood pressure monitoring if clinic systolic BP has been stable for visits 2 and 3 according to treatment assignment. If not, patients will return in 2-4 weeks for re-assessment of BP stability. Antihypertensive drug titration will be based on ambulatory BP from this point forward.
- Dispense medications for next 3 months

Visit 4 (6 months post-randomization) – Patients will return for evaluation of antihypertensive response to therapy according to randomized treatment group. Procedures previously defined above will be done at this visit:

- Medical history, concomitant medications, adverse events, medication compliance
- Standardized clinic BP measurements, body weight and height
- Antihypertensive medication titration or down-titration as appropriate – ad hoc ambulatory BP can be performed here to address therapeutic goals and if deemed medically necessary.
- Safety laboratory studies (potassium, creatinine, BUN) if clinically necessary

- Electrocardiogram if clinically necessary
- Dispense medications for next 6 months

Visit 5 (12 months post-randomization) – Patients will return for evaluation of antihypertensive response to therapy according to randomized treatment group. Procedures previously defined above will be done at this visit:

- Medical history, concomitant medications, adverse events, medication compliance
- Standardized clinic BP measurements, body weight and height
- Antihypertensive medication titration or down-titration as appropriate; ad hoc ambulatory BP can be performed here to address therapeutic goals and if deemed medically necessary.
- Laboratory studies (potassium, creatinine, BUN, glucose, ALT, cholesterol profile)
- Electrocardiogram if clinically necessary
- Home BP monitoring
- Dispense medications for next 6 months

Visit 6 (18 months post-randomization) – Patients will return for evaluation of antihypertensive response to therapy according to randomized treatment group and will have comprehensive testing for WMH, mobility, cognitive function as well as blood pressure control. Procedures previously defined above will be done at this visit:

- Medical history, concomitant medications, adverse events, medication compliance
- Standardized clinic BP measurements, body weight and height
- Antihypertensive medication titration or down-titration as appropriate; ambulatory BP will be performed to evaluate achievement of therapeutic goals according to randomized treatment strategy.
- Safety laboratory studies (potassium, creatinine, BUN) if clinically necessary

- Electrocardiogram
- MRI acquisition at UCONN neuroradiology
- Mobility Testing
- Cognitive Testing
- Questionnaires related to urinary function, QOL
- Home BP monitoring
- Dispense medications for next 6 months

Visit 7 (24 months post-randomization) – Patients will return for evaluation of antihypertensive response to therapy according to randomized treatment group. Procedures previously defined above will be done at this visit:

- Medical history, concomitant medications, adverse events, medication compliance
- Standardized clinic BP measurements, body weight and height
- Antihypertensive medication titration or down-titration as appropriate; ad hoc ambulatory BP can be performed here to address therapeutic goals and/or if deemed medically necessary.
- Safety laboratory studies (potassium, creatinine, BUN) if clinically necessary
- Electrocardiogram if clinically necessary
- Home BP monitoring
- Dispense medications for next 6 months

Visit 8 (30 months post-randomization) – Patients will return for evaluation of antihypertensive response to therapy according to randomized treatment group. Procedures previously defined above will be done at this visit:

- Medical history, concomitant medications, adverse events, medication compliance
- Standardized clinic BP measurements, body weight and height

- Antihypertensive medication titration or down-titration as appropriate; ad hoc ambulatory BP can be performed here to address therapeutic goals and/or if deemed medically necessary.
- Safety laboratory studies (potassium, creatinine, BUN) if clinically necessary
- Electrocardiogram if clinically necessary
- Home BP monitoring
- Dispense medications for next 6 months

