5.5 Schedule of Evaluations

Assessment during the randomized clinical trial of intensive versus standard ambulatory BP control

	Screen	Baseline		R A N D O M I Z E D	MONTH								Post Study	
		I	II		1	2	3	6	12	18	24	30		36
Med Hx-Phys Ex	X				X					X			X	
Med Washout (0 to 4 week period)		X	X											
ECG	X					PRN*	PRN	PRN	PRN	X	PRN	PRN	X	
CBC, Chemistries		X				PRN	PRN	X	X	X	X	PRN	X	
MRI	X									X			X	
Gait/Mobility			X							X			X	
Cognitive Tests			X							X			X	
Urinary Function		X								X			X	
Clinic BP,HR,BMI	X	X	X		X	X	X	X	X	X	X	X	X	X
Med Titration					X	X	PRN	X	PRN	PRN	PRN	PRN		
Adverse Events			X		X	X	X	X	X	X	X	X	X	X
ABPM (24hr)			X				X	X**		X			X	
HOME BP			X						X	X	X	X	X	

*PRN laboratory testing for safety checks only (electrolytes, and renal function tests); note: due to the age of patients, medical staff and PIs will be available at all times for impromptu visits; ** - if needed based on 3 month ABPM and/or changes in clinic BP

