5.6 Description of Evaluations

Resting clinic BP: Taken on a semi-automated digital device (Suntech TM2420, Morrisville, NC) with an appropriate cuff. After sitting 5 min, BP will be taken twice, 2-3 minutes apart in the non-dominant arm and averaged. BP readings will be taken between 8 and 11 am, before taking antihypertensive medication.

24-hour ambulatory BP Monitoring (ABPM): conducted after antihypertensive washout and prior to initiation of investigative therapy using the Oscar II BP device (Suntech Medical Instruments, Morrisville, NC) which has been validated independently.¹⁸ The device is a light, comfortable automated BP recorder. Eighty BP

readings will be programmed during the 24-h study. Monitors will measure BP and heart rate every 15 min from 6 am to 10 pm, and every 30 min from 10 pm to 6 am.^{19, 20.}

Follow-up ambulatory BP recordings will be made at 3 months to evaluate response to therapy and at 6 months if medications were adjusted at 3 months to ascertain if systolic BP goals were achieved. Data will be transferred to Accuwin software program (Suntech Medical Instruments, Morrisville, NC) for analysis. Components of the ABPM for analysis will include the 24-hour mean systolic and diastolic BP, the awake and sleep BPs, and the early morning BP (the difference between the 2 hour post-awakening BP – the 2 hour pre-awakening BP) as previously described.^{20, 21.}

A baseline electrocardiogram (ECG): a standard 12-lead ECG will be obtained at baseline, 18 months and end of study – these will be assessed by study physicians [name] and/or [name].

Laboratory tests (safety): CBC, glucose, BUN, creatinine, liver enzymes and urinalysis, sodium and potassium. Abnormal results will require further testing or referral for treatment before (or in lieu of) study participation.

Laboratory tests (research): lipid profile (Total, HDL and LDL cholesterol, and triglycerides).

Mobility Measures: Performance will be assessed primarily by timing.

- walking-moving
- Gait Speed: Gait speed will be measured as participants walk at a comfortable pace over an 8-meter course with 1 meter for acceleration and deceleration.
- Stair Ascent/Descent: stair ascent and descent will be used as a measure of walking-moving. We have previously shown stair descent time to be predicted by WMH²². Ascent and descent of 4 steps at a comfortable pace will be timed separately.

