5.7 Specification of Safety Parameters

There are no experimental antihypertensive drugs in the trial. All medications that will be used are quite mature and have been in clinical use for > 15 years. Due to the age of the study patients, a number of serious and non-serious adverse events are expected and will be tabulated according to treatment assignment. Should a study patient have symptoms suggestive of vertebrobasilar insufficiency, whether prior to enrollment or during follow-up, the patient will be evaluated by a neurologist. All discontinuations due to serious and non-serious adverse events will be tabulated according to treatment assignment as well. These include:

Serious Adverse Events

- Major adverse cardiovascular events: cardiovascular death, nonfatal myocardial infarction, nonfatal stroke, unstable angina with urgent revascularization.
- Cardiac arrhythmias not associated with ischemia
- Hospitalized congestive heart failure
- Falls and/or syncope associated with injury (e.g fractures)
- Non-cardiovascular death
- Venous thromboembolic events (pulmonary embolism, deep venous thrombosis)
- Aortic aneurysm rupture, surgery
- Peripheral arterial surgery
- Coronary and peripheral revascularization, elective
- Major life-threatening infections

Non-Serious Adverse Events

- Potential symptoms/signs of low systolic BP (recorded systolic BP < 90 mmHg, postural reduction in systolic BP > 20 mmHg, lightheadedness, near syncope, falls without injury)
- Non-serious or non-severe adverse events according to body system: allergic, hematologic, gastrointestinal, pulmonary, renal, etc.)

Safety laboratory parameters

The key safety laboratory studies in the trial will include: hematocrit, potassium, sodium, creatinine, blood urea nitrogen, glucose, and AST. Each laboratory parameter will be evaluated in context of the individual patient. In general, large changes (e.g. doubling of serum creatinine) will be evaluated immediately, whereas small changes (e.g. a 15% increase in serum creatinine from baseline) will be repeated in a convenient fashion for the patient. Potassium supplements will be prescribed as needed.

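### The schedule table fixes chemistry draws at months 6, 12, 18, 24 and 36, but the visit text fixes only month 12 and leaves the other four to clinical judgement

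*Protocol*

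**What the plan says.** The schedule in protocol section 5.5 has a row headed "CBC, Chemistries". It carries an X at Baseline I and at months 6, 12, 18, 24 and 36, PRN at months 2, 3 and 30, and nothing at month 1. A footnote explains the PRN code: "PRN laboratory testing for safety checks only (electrolytes, and renal function tests".

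The visit lists give a different rule. Visit 5 (month 12) is the only follow-up visit with laboratory tests listed without a condition: "Laboratory studies (potassium, creatinine, BUN, glucose, ALT, cholesterol profile". Visit 4 (month 6), Visit 6 (month 18) and Visit 7 (month 24) in 5.6.3, and Visit 9 (month 36) in 5.6.4, read "Safety laboratory studies (potassium, creatinine, BUN) if clinically necessary". The same line appears at months 2, 3 and 30.

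Section 5.6 defines the safety panel as "CBC, glucose, BUN, creatinine, liver enzymes and urinalysis, sodium and potassium", without timing. Section 5.7 states: "The key safety laboratory studies in the trial will include: hematocrit, potassium, sodium, creatinine, blood urea nitrogen, glucose, and AST". It also sets actions on change from baseline. A doubling of creatinine is to be evaluated at once, while "small changes (e.g. a 15% increase in serum creatinine from baseline) will be repeated in a convenient fashion for the patient".

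**The concern.** A site cannot follow both instructions. Under the table, every patient has blood drawn at five fixed points after randomization. Under the visit text, four of those five depend on someone judging the test necessary.

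Patients are 75 or older. Under section 5.1 both arms start on lisinopril (an ARB if it is not tolerated), with doses titrated upward; a diuretic comes next if the goal is not met, and an aldosterone antagonist is among the permitted additions after that. Section 6 names hyperkalemia and hyponatremia among possible reasons for stopping the intensive treatment. The creatinine rules in 5.7 can operate only if a sample is taken. A rising creatinine or potassium may cause no symptoms, and a draw prompted by clinical need is the kind least likely to find it. What is at stake is uniform safety surveillance of the individual patient.

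**Working it through.** No figure in the plan needs reproducing. The check sets the table row against the visit lists and counts.

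| Month (visit) | Table, 5.5 | Visit text, 5.6.3 and 5.6.4 | Agree? |
|---|---|---|---|
| 1 (Visit 1) | blank | no laboratory tests listed | yes |
| 2 (Visit 2) | PRN | conditional | yes |
| 3 (Visit 3) | PRN | conditional | yes |
| 6 (Visit 4) | X | conditional | **no** |
| 12 (Visit 5) | X | unconditional | yes |
| 18 (Visit 6) | X | conditional | **no** |
| 24 (Visit 7) | X | conditional | **no** |
| 30 (Visit 8) | PRN | conditional | yes |
| 36 (Visit 9) | X | conditional | **no** |

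**Is the column alignment trustworthy?** The ECG row uses the same two codes: X at months 18 and 36, PRN at 2, 3, 6, 12, 24 and 30. The visit text agrees with it at every visit. The MRI row (screening, 18, 36) and the ABPM row (baseline, 3, 6 if needed, 18, 36) also fall where expected. The mismatch is therefore in the laboratory row and not in how the table was read.

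**Can X be read as conditional?** No. X and PRN are separate codes within one row, and the conditional wording in the text matches PRN at months 2, 3 and 30.

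**Size of the difference**

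- Fixed draws after randomization: table {6, 12, 18, 24, 36} = 5; text {12} = 1.
- Scheduled draws in conflict: {6, 18, 24, 36} = 4 of 5.
- First fixed potassium and creatinine on treatment: month 6 (table) or month 12 (text).
- Intervals under the table: 6 − 0 = 6, 12 − 6 = 6, 18 − 12 = 6, 24 − 18 = 6 and 36 − 24 = 12 months. The longest is 12 months.
- Intervals under the text: 12 − 0 = 12 months, then 36 − 12 = 24 months with no fixed draw, the final visit included.
- Extra panels if the text was being followed and the table is adopted: 4 per patient. The ceiling for 200 randomized patients is 4 × 200 = 800. For the 140 projected completers it is 4 × 140 = 560.

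**The case against.** **The conditional line may be an addition to a routine panel.** It resembles the as-needed item in the table footnote, so it might sit on top of a routine draw that the table requires. This is weak. At Visit 5 the routine panel replaces the conditional line, and no routine panel is listed at the four visits in question.

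**Consistency could be restored the other way.** Changing four X cells to PRN would also remove the conflict, and the documents do not show which source is in error. That stands. The preference for the table rests on safety and low cost, not on proof of what was intended.

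**The consequence is limited.** The drugs are long established, section 6 calls the electrolyte problems rare, staff are available for impromptu visits, and as-needed testing exists under either rule. All of this stands and keeps the point modest. It does not cover the patient without symptoms.

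Two stronger readings are tempting, and the documents do not support them:

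- *That laboratory comparisons between arms will be biased.* Clinical staff know the assignment, so testing frequency could differ by arm. But neither document plans a by-arm laboratory comparison: the SAP has no laboratory endpoint, and section 5.9 sends the DSMB aggregate data without saying by arm. Testing rates are not given, and testing by indication does not turn unequal testing into a proportionate excess of detected cases.
- *That sodium, potassium or hematocrit are missing from the plan.* The visit lists are short; Baseline visit 1, for example, "includes complete blood count, serum creatinine and blood urea nitrogen, glucose, ALT, urinalysis" with lipids but no electrolytes. The general panel in 5.6 covers blood count, sodium, potassium and liver enzymes, so the short lists may be shorthand.

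**Conclusion.** The point holds as an internal contradiction about timing. The table and the visit text disagree at four of five scheduled chemistry draws, and nothing in the protocol or SAP settles which applies. If the text is followed, fixed draws fall from five to one, the first moves from month 6 to month 12, and the longest stretch without one doubles from 12 to 24 months. Creatinine changes that 5.7 is meant to act on, and the potassium and sodium problems in section 6, could then go unseen in patients without symptoms.

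This assumes that the visit lists are used as working instructions. If staff follow the table, nothing is lost beyond clarity. A reader might infer that patients were in fact under-monitored, but the documents do not show which rule was used. The primary gait comparison is not affected. It is worth correcting because it is cheap, and it ranks as a modest safety point.

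**What to change.** At Visits 4, 6 and 7 (section 5.6.3) and Visit 9 (section 5.6.4), remove the clinical-necessity condition from the laboratory line. List a scheduled draw for all patients, matching the table and using the safety panel already defined in 5.6 and 5.7. Keep months 2, 3 and 30 as-needed. State that the 5.5 table governs if any difference remains.

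The cost is wording only if the table is already followed. Otherwise it is up to four more basic panels per patient at visits that already take place. No new visit, scan, ambulatory recording or outcome test is required.
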